##### ***Data analysis for Jacobi site***

Construction of epithelium maps by mLCI: Maps of the cervix delineating the T-zone will be created from each subject's mLCI data. The extent of columnar and squamous epithelia will be reported as a percentage of the image of the epithelium. Each scan in the 36 point field will initially be reviewed manually to determine the epithelium type based on the depth-resolved reflection profile for that point. The presence of clear histological layers is indicative of squamous epithelium while a thinner layer with less structure indicates columnar epithelium [22]. As we compile a database of mLCI maps of the cervix, we will develop automated algorithms for assessing epithelial types and transitions by using cluster analysis to discriminate scans. The mLCI maps will be compared to digital colpophotography analysis to assess accuracy.

Measurement of epithelial areas by colpophotography: Digital colpophotographs will be viewed in Adobe Photoshop for quantitative computerized planimetry as previously published [23, 24]. We will manually outline all areas of columnar, metaplastic and squamous epithelia and the total visible cervical face. Total pixel counts of the various epithelial types will be calculated and ectopy expressed as percentage of the total cervix.

Correlation of mLCI images to colpophotographs and detailed written maps: The mLCI epithelial maps will be visually compared to colpophotographs to achieve co-registration. This is feasible based on the relatively modest number of patients in the study. The written map and white light imaging via the probe will aid in coregistration. We will correlate mLCI readings with calculated areas of epithelial types (pixel counts and percentage). Biostatistical analyses will address covariates including age, infections, cytology, menstrual cycle, and sexual behaviors.

Potential problems, alternative strategies, and benchmarks for success: The mLCI approach will be viewed as successful if there is less than average absolute difference of 10% in the area estimate compared with manual analysis.

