[name], the Duke PI of this study, is the primary awardee of the NIH grant supporting this work. [name] and his team have developed the LCI research devices and will conduct small studies at Duke (described below) to assess if any adjustments to the devices are needed before they are sent to Jacobi Medical Center for the larger studies. The studies at Jacobi Medical Center will be funded as a subaward / consortium agreement of [name] NIH grant.

Duke will recruit up to 15 women to enroll in stages 1 and 2 of the study, in order to achieve the target number of 10 subjects who complete each stage. This gives a total enrollment of up to 30 subjects at Duke to complete both stages of the study at that site.

Jacobi will enroll up to 100 women for stage 1, in order to achieve the target number of 40 women who complete stage 1. For stage 2 of the study, Jacobi will enroll up to 140 women in order to achieve the target number of 70 women who complete that stage.

Data from both sites will be analyzed at Duke. Study conduct at Duke will be under the oversight of the IRB of the Duke University Health System. Study conduct at Jacobi Medical Center will be under the oversight of the IRB of the Albert Einstein College of Medicine and Montefiore Medical Center.

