#### **Stage 1 Study Procedures for subjects at Jacobi**

Subjects will be informed of the study when they present to the clinic for a regular clinical care visit. If interested in participating, subjects will complete the following study-related procedures in addition to the standard of care visit procedures.

- Read consent form
- Ask / answer questions
- Sign consent form
- Urine pregnancy test – must be negative before imaging can occur
- Colpophotography of cervix to compare with mLCI data
- mLCI examination of the cervix (with speculum)

We will obtain written informed consent and confirm eligibility criteria. Data collection will include a brief medical history and pregnancy testing.

The doctor will then insert a speculum in order to directly visualize the cervix. Colpophotographs will be taken to compare to mLCI data during data analysis. The doctor will then gently place the mLCI probe against the cervix. White light camera visualization, incorporated into the mLCI probe, will guide the probe positioning by the clinician to confirm contact with the cervical epithelium. The probe will then be held in place for mLCI data acquisition for up to 1 minute. When data collection is completed, the mLCI probe will be removed and placed on a custom holder that prevents the contact portions of the probe from coming into contact with contaminating surfaces.

The doctor will then continue with the rest of the patient's standard of care visit procedures.

At some visits, the physician may choose to make an additional measurement with the mLCI device, by inserting it without a speculum and using the white light camera (incorporated into the mLCI probe) for visual guidance to position the probe. Comparing measurements made by inserting the mLCI device with and without a speculum will allow us to determine if the white light visualization by the camera is sufficient to correctly place the probe over the cervix without having to use a speculum in future studies.

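### Stage 1 at Jacobi: the comparison of mLCI with the colpophotograph reports no signed difference, and part of it uses raw pixel counts that are not on the scale of the mLCI percentages

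*Combined protocol and SAP*

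**What the plan says.** The Stage 1 section headed Data analysis for Jacobi site describes the two instruments on different scales. For mLCI: "The extent of columnar and squamous epithelia will be reported as a percentage of the image of the epithelium". For the photograph, columnar, metaplastic and squamous areas are outlined by hand, and "Total pixel counts of the various epithelial types will be calculated and ectopy expressed as percentage of the total cervix".

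The aim is stated generally, with no statistic attached: "The mLCI maps will be compared to digital colpophotography analysis to assess accuracy". Two quantitative comparisons follow:

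- Correlation: "We will correlate mLCI readings with calculated areas of epithelial types (pixel counts and percentage". No coefficient is named.
- A success benchmark: "less than average absolute difference of 10% in the area estimate compared with manual analysis". I take the manual analysis to be the hand outlining of the photograph.

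A further comparison is visual: "The mLCI epithelial maps will be visually compared to colpophotographs to achieve co-registration".

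The documents nowhere plan a signed difference, limits of agreement, a regression intercept and slope, or a point-by-point classification table. The section on Stage 1 procedures at Jacobi gives the purpose of the photographs ("Colpophotographs will be taken to compare to mLCI data during data analysis") but no fixed distance, zoom or scale marker. On size, the Purpose section says: "Jacobi will enroll up to 100 women for stage 1, in order to achieve the target number of 40 women who complete stage 1".

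**The concern.** When one measurement method is checked against another, two questions matter: does it read high or low on average, and how widely do individual differences spread? Correlation answers neither, because it measures association. A mean of unsigned differences combines the two into one number. The distinction matters at this stage because the remedies differ: a consistent over-call of columnar tissue points to the rule for reading the depth profile, whereas scatter points to sampling, placement or co-registration.

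A one-directional error is plausible. Each of the 36 points is first classed by a judgement on whether its layers are clear or thin, and the photograph has a metaplastic class that the mLCI report lacks.

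The pixel-count correlation raises a second issue. A pixel count depends on how large the cervix appears in the frame as well as on the tissue. If magnification differs between women, this correlation could look weak for reasons unrelated to the device.

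**Working it through.** **Inputs from the documents.** Benchmark 10% (taken as percentage points of area); 36 points per map; 40 completers. The plan gives no SD, bias, magnification figure or derivation of the 10% or the 40, so there is no planned figure to reproduce. Every bias, SD and magnification value below is an assumption.

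**1. Mean absolute difference.** For normally distributed differences with mean bias b and SD s:

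MAD = s·√(2/π)·exp(-b²/(2s²)) + |b|·(1 - 2Φ(-|b|/s))

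For b = +8 or -8 and s = 4: 4 × 0.798 × exp(-2) + 8 × (1 - 2 × 0.02275) = 0.43 + 7.64 = 8.07.

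| Bias b | SD s | MAD | b ± 1.96s | Benchmark |
|---|---|---|---|---|
| +8 | 4 | 8.07 | 0.2 to 15.8 | pass |
| -8 | 4 | 8.07 | -15.8 to -0.2 | pass |
| 0 | 10 | 7.98 | -19.6 to 19.6 | pass |
| +8 | 2 | 8.00 | 4.1 to 11.9 | pass |
| +5 | 8 | 7.59 | -10.7 to 20.7 | pass |
| +10 | 4 | 10.02 | 2.2 to 17.8 | fail |
| +12 | 4 | 12.0 | 4.2 to 19.8 | fail |

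The first four rows have nearly the same MAD but describe different error patterns. The last two show the limit of the point: the mean of |d| can never be smaller than |mean of d|, so a mean bias of 10 or more fails.

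**2. Correlation.** If the reading is true area + b + error, then r = SD(true)/√(SD(true)² + s²), which does not contain b. With s = 4 and a true-area SD of 10, 15 or 20 points, r = 10/√116 = 0.93, 15/√241 = 0.97 or 20/√416 = 0.98. Simulation with b = 0, +8 and -8 gave the same values in each case.

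**3. Pixel counts.** Let f be the true columnar share with CV c, and let the linear magnification be log-normal with SD σ on the log scale. The pixel count is then proportional to f × magnification². For a perfect mLCI percentage:

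r(f, pixels) = c/√((1 + c²)·exp(4σ²) - 1)

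With c = 0.5 assumed (simulated with a mean share of 30%), this is 0.5/√(1.25·exp(4σ²) - 1):

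| σ | 10% | 15% | 20% | 30% |
|---|---|---|---|---|
| r | 0.91 | 0.82 | 0.73 | 0.56 |

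Against the photographic percentage, the same perfect reading has r = 1 at every σ, because magnification cancels in a ratio of areas from one image.

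**4. What 40 women would give.** The 95% half-width for the mean signed difference is t(0.975, 39)·s/√40. For each limit of agreement it is about t(0.975, 39)·s·√(1/40 + 1.96²/(2 × 39)).

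| Assumed SD of differences | 2 | 4 | 8 | 10 |
|---|---|---|---|---|
| Half-width, mean bias (points) | 0.64 | 1.28 | 2.56 | 3.20 |
| Half-width, each limit (points) | 1.1 | 2.2 | 4.4 | 5.5 |

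One grid point is 100/36 = 2.8 percentage points. With an SD up to 8, 40 women therefore estimate mean bias to within about one grid point.

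**The case against.** The strongest reply is that the only success criterion is already a measure of agreement and limits bias, so any bias that passes lies inside an error the protocol has declared acceptable. That stands. A reader might infer that a device with a large constant bias could pass; the arithmetic above rules this out for a mean bias of 10 or more. What remains unreported is the direction of a smaller error and its split between bias and scatter.

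A second reply is that pixel counts may be only the step towards a percentage, that no success decision uses their correlation, and that the outlining follows published methods which may standardise scale. Those sources cannot be seen here, and the documents do not say that magnification varies. This makes the pixel-count part conditional. Even so, the sentence as written lists counts beside percentages as quantities to be correlated.

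A third reply is that the visual comparison might reveal a consistent over-call, and that the signed differences can be recovered from the planned data. Both are fair. But the visual step is there for co-registration, and recoverable is not the same as planned.

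A reader might also infer that an unseen bias would be carried into the automated algorithm. The documents do not support this: the algorithm is described as cluster analysis of scans, and nothing ties it to the area comparison. Stage 2 maps with OCT and has its own benchmark against colpophotography.

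Finally, a signed difference on its own would not isolate device bias. The two percentages have different denominators, and two tissue classes are set against three. This is correct and shapes the remedy.

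**Conclusion.** The point holds as a modest weakness in an early feasibility analysis. The planned measures can show that total average error is under 10 points, but not which way the device errs or whether the error is systematic. The conclusion about correlation and sign is algebraic and does not depend on the assumed SDs; those only illustrate it. It does rest on reading the benchmark as the mean of unsigned differences in percentage points. If the word absolute was meant to say points rather than relative percent, signed errors could cancel in the average and scatter would be the hidden part, so the term needs defining in either case.

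The pixel-count loss depends on assumed variation in magnification and on the assumed spread of columnar share. No pass or fail decision rests on that correlation.

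**What to change.** In the Stage 1 section on data analysis for the Jacobi site:

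1. Make the comparison on percentages only, and drop the correlation with raw pixel counts.
2. Report the mean signed difference, mLCI minus photograph, in percentage points with its 95% CI, and Bland-Altman 95% limits of agreement, beside the existing benchmark. Correlation on percentages may stay as a secondary description.
3. Define the benchmark as the mean of unsigned differences in percentage points, if that is what is meant.
4. Compute both percentages with matching tissue classes, stating where metaplastic tissue is counted, and over the same field as far as co-registration allows. State any mismatch that remains, since the signed difference will include it.

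The cost is a change of wording and a little extra analysis. No new visits, measurements or participants are needed.

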## Design & Procedures

### ***STAGE 1: mLCI device development***

#### **mLCI instrument description**

The purpose of this instrument is to obtain optical measurements from the cervix via a vaginal probe to create a map of the surface cells that distinguishes the ectocervical and endocervical epithelia. The boundary between the two cell types is known as the squamocolumnar junction, or “t-zone”, which is the transitional region at which cervical dysplasia is most likely to occur.

The instrument delivers infrared light to 36 locations on the cervix, and measures the depth-profile of back-scattered light from each location using low coherence interferometry (LCI). This technique is thus termed multiplexed LCI (mLCI). The LCI profile data is stored by a computer for subsequent analysis to identify cell type.

The components of the mLCI instrument are grouped in the following modules: 1) Optical probe, 2) mLCI interferometer, 3) white light imaging module, 4) computer, and 5) physical enclosure.

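### The Stage 1 success rule at Jacobi scores only epithelial area, so it can be met without showing that mLCI locates the squamocolumnar junction

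*Combined protocol and SAP*

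**What the plan says.** The Combined protocol and SAP gives Stage 1 a spatial aim. The Purpose of the Study and the mLCI instrument description both ask for a map that separates ectocervical from endocervical epithelium and shows the junction between them. The Stage 1 section Data analysis for Jacobi site says "Maps of the cervix delineating the T-zone will be created" for each subject.

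That section then turns the maps into totals. For the device, "The extent of columnar and squamous epithelia will be reported as a percentage of the image of the epithelium". For the reference photograph, "Total pixel counts of the various epithelial types will be calculated", with "ectopy expressed as percentage of the total cervix". The maps are compared with colpophotographs by eye to co-register them, helped by a written map and the probe's white-light image, and the plan speaks of a comparison to assess accuracy. For the numerical link it says "We will correlate mLCI readings with calculated areas of epithelial types".

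The only success criterion is "less than average absolute difference of 10% in the area estimate", judged against manual analysis. No criterion refers to position, to agreement point by point, or to the size of the correlation.

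**The concern.** The aim is to show where one epithelium ends and the other begins. The benchmark measures how much of each there is. A map can be right on the second and wrong on the first, because errors in opposite directions offset each other in a total. The planned correlation uses the same totals and is equally blind to position.

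At stake is the meaning of a Stage 1 success. The Purpose of the Study says the larger Jacobi studies are to determine how well the devices tell the epithelial types apart. A pass on area alone does not answer that for location.

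**Working it through.** **Inputs from the documents.** "The instrument delivers infrared light to 36 locations on the cervix", so one point is 1/36 = 2.8% of the map and 10% is 3.6 points. The target is 40 completers, which gives up to 40 × 36 = 1,440 points. The threshold is 10%. It is chosen, not derived, so there is no plan figure to reproduce.

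**Not in the documents.** The mean and the between-woman spread of ectopy are not given, nor is whether 10% means percentage points or a relative error. Values for these are assumptions below.

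**1. Right total, wrong place (no distributional assumption).** Let c of 36 points be columnar and let the map place c columnar points elsewhere with no overlap. The area difference is (c − c)/36 = 0 and 2c points are wrong.

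| Case | Area difference | Points wrong | Columnar points found | Squamous points found |
|---|---|---|---|---|
| c = 11, all misplaced | 0 | 22/36 (61%) | 0/11 | 14/25 (56%) |
| c = 9, a 3×3 block moved two rows and two columns (6×6 grid assumed) | 0 | 16/36 (44%) | 1/9 | 19/27 (70%) |
| c = 18, left and right halves swapped | 0 | 36/36 | 0/18 | 0/18 |

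All three score a perfect zero, whether 10% is absolute or relative. In the second row Cohen's kappa is (0.556 − 0.625)/(1 − 0.625) = −0.19, worse than chance.

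**2. Cancelling errors (illustration).** Take sensitivity 60% and specificity 90% for columnar points, independent point errors, and 10% read as percentage points. For a woman with ectopy p, the expected device area is 0.6p + 0.1(1 − p) = 0.1 + 0.5p, so the bias is −0.5(p − 0.2). It is zero at p = 20% and grows as p moves away from that.

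- Every woman at 20%: SD = √(7.2×0.6×0.4 + 28.8×0.1×0.9)/36 = 0.058, and the mean absolute difference is 0.798 × 0.058 = 4.6 points. If the 36 points are instead a random sample of a cervix with 20% ectopy, it is 0.798 × √(0.2×0.8/36) = 5.3. Either way it is about 5.
- Ectopy varying between women (beta distribution, mean 20%, points sampled, simulated): 7.0 points at SD 12, 8.1 at SD 16, 10.9 at SD 25.

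The device is expected to pass at the first three settings and to fail at SD 25, while missing 40% of columnar points throughout. Errors that cluster within a woman would raise these figures. Under a relative reading it fails: 4.6/20 = 23%.

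**3. Constant output (conditional).** With normally distributed ectopy, a constant at the median has expected error 0.798 × SD, which is below 10 points when SD < 10/0.798 = 12.5. Simulated chance of passing with 40 women:

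| SD (points) | 10 | 12 | 12.5 | 15 | 20 |
|---|---|---|---|---|---|
| Pass | 98% | 65% | 52% | 8% | <0.1% |

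With a beta distribution of mean 20% and the constant set at the mean, it passes about 64% of the time at SD 12 and 2% at SD 16. With a beta mean of 10% and the constant at the median, it passes 83% of the time at SD 12.5 and 65% at SD 15. An all-squamous output has error equal to mean ectopy, so it is expected to pass only if that mean is below 10%. If 10% is relative to each woman's own area, the constant passes in 2% or fewer of the simulated cases.

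**The case against.** The strongest reply is that the plan is not blind to location. It makes a T-zone map for each woman, registers it by eye to the photograph with two further aids, and announces a comparison to assess accuracy. That stands, and a reader who inferred that Stage 1 will yield no evidence on location would be wrong. But no agreement measure follows from these steps and none of them decides success.

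A second reply is that nothing in Stage 2 depends on a Stage 1 pass. A reader might infer that a misplaced mLCI map would misdirect the later nuclear measurements. The documents do not support this. The Purpose of the Study and the Scanning a/LCI instrument description say that Stage 2 makes its own OCT map, and its measurement sites may also be chosen by the user. The harm is confined to the Stage 1 conclusion.

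A third is that this is preliminary work with a development milestone and no hypothesis test, and that total misplacement is a constructed case for which the documents suggest no mechanism. That is fair and limits the severity: the data stay usable and can be reanalysed. It does not change what the milestone measures.

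Finally, point agreement can flatter the device. If maps are aligned by matching them to the photographs, agreement computed afterwards is partly circular. This stands and shapes the fix.

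**Conclusion.** The point holds and should be acted on. That the area rule ignores location follows from its wording, with no assumption about ectopy and under either reading of 10%. Success can therefore be declared without showing that mLCI finds the squamocolumnar junction. Nothing here shows that the device does misplace it.

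The cancellation example is an illustration. It needs 10% to mean percentage points, mean ectopy of 20% and independent errors, and it turns into a fail at SD 25.

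A reader might also infer that a device giving every woman the same answer would pass. The documents do not establish that. It needs percentage points, a constant near the centre, and either an SD of roughly 12 points or less or a low mean. The plan states no spread.

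One further ambiguity should be settled. Manual analysis may mean the outlined photographs or the hand reading of the mLCI scans. If it means the latter, the rule does not involve the photograph at all.

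**What to change.** Keep the area criterion, state whether 10% is absolute or relative and what manual analysis refers to, and add the following to the success rule.

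1. **Location.** Over the (up to) 36 co-registered points per woman, report sensitivity for columnar and for squamous points against the colpophotograph, with confidence intervals clustered by woman. The sponsor should set the required values before the analysis; the documents give no basis for choosing them here. Every map in the first table would show up on this measure.
2. **Registration.** Fix it from the white-light image and the written map before the mLCI map is seen, not by matching that map to the photograph. State how metaplastic areas are classed, since they are outlined on the photograph but are not a category in the mLCI reading.
3. **Reference prediction.** Require the area error to be smaller than that of a constant prediction, both all-squamous and mean ectopy.

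Keep the planned correlation, because a constant output has no covariance with the reference and is exposed by it. Put the Bland-Altman mean difference and limits of agreement beside it. They should not replace it: a constant at the mean has zero mean difference, and its limits reflect only the spread of ectopy.

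The cost is modest extra analysis, with no added visit or examination. Two practical points need confirming: that white-light frames are saved (the instrument description says they are digitised and displayed), and when the written map is made (it is not in the Stage 1 Jacobi procedures). The real price is a success claim that is harder to meet.
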